Clinimark [name]	TITLE: Clinical Evaluation of the Zynex Monitoring System, Model CM-1600 ID# PR 2022-516 Principal Investigator: [name] Site ID # 001	DOCUMENT NUMBER PR# 2022-516 SHEET 21 of 30	REV 1
---	--	--	-------

Confidential & Proprietary to Clinimark, LLC.

CLINIMARK Test Plan

Clinical Evaluation of Zynex Monitoring System, Model CM-1600 PR2022-516

- Clinimark Control # B3000-000-003 – Adverse Events and Protocol Deviation Reporting System
- Clinimark Control # F2000-001-029 - Device Deficiency Form
- Clinimark Control # F2000-001-016 - Device Accountability Form
- Clinimark Control # F2000-001-015 - Delegation of Authority
- Clinimark Control # F2000-001-017 - Investigator Financial Interest Disclosure
- Clinimark Control # F2000-001-022 – Investigator’s Certification Statement
- Clinimark Control # F2000-001-028 - Participant Enrollment Log
- Clinimark Control # F2000-001-027 - Site Personnel Training Log
- Clinimark Control # F2000-001-033 - Site Visit/ Monitoring Log
- Clinimark Control # F2000-001-034 - Data Clarification Form
- Clinimark Control # F2000-001-037 - Protocol Deviation Log
- Clinimark Control # F2000-001-038 - Adverse Events Log
- Clinimark Control # F2000-001-042 - Adverse Event CRF
- Clinimark Control # F2000-001-043 - Protocol Deviation Form
- Communications
- Zynex Monitoring Solutions CM-1600 Instructions for Use (Rev 6)

Current revision of documents applies.

Amendments to the Clinical Investigation Plan

Zynex or the site may need to make protocol changes during the study. Such amendments will be documented and reviewed, and changes will be submitted to Zynex for first approval, then to the IRB for approval. Zynex and the site will decide whether or not to continue to enroll participants during this time. The site may proceed with the amendment upon receipt of IRB approval.

Deviations from the Clinical Investigation Plan

Investigators are not allowed to deviate from the Clinical Investigation Plan (CIP) except under emergency circumstances. Deviations from the CIP to protect the rights, safety, and wellbeing of human participants may proceed without prior approval of the Sponsor or the IRB. Such deviations shall be documented and reported to the Sponsor and the IRB as soon as possible but within 5 working days of the occurrence of such deviation.

Deviations that significantly affect the safety, efficacy, integrity, or conduct of the study must be reported to the Sponsor within 5 working days from awareness of occurrence and reported to the IRB per the deviation reporting policy.

Deviations that do not affect the safety, efficacy, integrity, or conduct of the study will be documented in the case report forms, regulatory binder Protocol Deviation Log as appropriate.

Device Accountability

A Device Accountability Log will be maintained for the Sponsor’s equipment, documenting date of receipt, description of device (including model number, lot number, serial number or unique code, and quantity) and date of return for used and unused product. Device usage will be recorded in the Case Report Form for each individual participant.

Packaging and Labeling

Research conducted for this study will utilize investigational devices and devices cleared through the 510k regulatory process. The Sponsor is responsible for packaging and labeling the device for delivery to the study site. FDA cleared devices do not require special labeling. Investigational devices or their immediate packages shall bear a label with the following information: name and place of the manufacturer, packager, or distributor, the quantity of contents, if appropriate, and the following statement:

Clinimark [name]	TITLE: Clinical Evaluation of the Zynex Monitoring System, Model CM- 1600 ID# PR 2022-516 Principal Investigator: [name] Site ID # 001	DOCUMENT NUMBER PR# 2022-516 SHEET 22 of 30	REV 1
---	--	--	-------

Confidential & Proprietary to Clinimark, LLC.

CLINIMARK Test Plan
Clinical Evaluation of Zynex Monitoring System, Model CM-1600
PR2022-516

“CAUTION - Investigational device. Limited by Federal (or United States) law to investigational use.”

The label or other labeling shall describe all relevant contraindications, hazards, adverse effects, interfering substances or devices, warnings, and precautions.

It is the Investigator’s responsibility to ensure that the appropriate labeling is visible and remains intact throughout the life of the study.

The Instructions for Use (IFUs) are provided as separate documents from this protocol.

Storage and Accountability

The site will store the investigational product. The storage area should be locked/secure with access limited only to approved study staff.

The site will record and track usage of the investigational device by each participant. Documentation should verify that the device use was in accordance with the approved protocol. The Equipment Document in the Case Report Form shall provide documentation of the devices used on the study participant(s).

Cleaning

Please refer to CM-1600 Instructions for Use.

Statement of Compliance

The study will be conducted in accordance with the Declaration of Helsinki, 21 CFR 50, and 21 CFR 812 for non-significant risk device study investigations. The study will not commence until the approval has been received from the IRB.

[REDACTED]

Clinimark [name]	TITLE: Clinical Evaluation of the Zynex Monitoring System, Model CM-1600 ID# PR 2022-516 Principal Investigator: [name] Site ID # 001	DOCUMENT NUMBER PR# 2022-516 SHEET 23 of 30	REV 1
---	--	--	-------

CLINIMARK Test Plan
Clinical Evaluation of Zynex Monitoring System, Model CM-1600
PR2022-516

Informed Consent Process

- The Principal Investigator or his / her designee conducts the informed consent process.
- Verify that the participant acknowledges ability to read English.
- Instruct the participant to ask questions at any time during this process, especially about things they do not understand.
- Allow participant ample time to read the entire form and ask questions
- Give a thorough description of the study and the participant’s involvement, with particular emphasis that they may withdraw from the study at any time.
- After the participant has read the form, ask if he/she understands everything.
- Ask if he/she would like to take part in the study, and if so, ask him/her to sign and date the form.
- Once the participant has signed and dated the informed consent, the Principal Investigator or authorized designee will sign and date the form.
- Give a copy of the informed consent to the participant.
- No procedure may be performed before the informed consent is signed by the participant.

If an Investigator uses a device without obtaining informed consent, the Investigator shall report such use to the Sponsor and the reviewing IRB within 5 working days after the use occurs.

Safety

Investigators

All experimenters must review the protocol prior to test and sign that they read and understood the contents.

Participant

Equipment is checked out for proper functionality prior to being placed on the participant.

The participant or legal guardian of the participant will review and sign the informed consent following a discussion of the test procedure; after all questions regarding the study have been answered; and prior to the start of any study procedures. The participant will complete the health assessment questionnaire and disclose any pertinent issues that may affect his/her health during the test. The participant or legal guardians of the participant may withdraw the participant from the study at any time. The participant may be withdrawn per the Procedure section below.

A clinician will be present to monitor the participant at all times. Safety monitoring includes ECG, SpO₂, pulse rate, respiration rate, direct observation and communication with the participant.

Adverse Event Definitions

The definitions for adverse event, adverse device effect, serious adverse event, serious adverse device effect, unanticipated adverse device effect, and their classifications are provided below (ISO 14155, 21 CFR 812.3).

- **Adverse Device Effect (ADE):** Adverse event related to the use of an investigational medical device and resulting from insufficiencies or inadequacies in the instructions for use, the deployment, installation, the operation, any malfunction of the investigational medical device, or from usage error.

Clinimark [name]	TITLE: Clinical Evaluation of the Zynex Monitoring System, Model CM-1600 ID# PR 2022-516 Principal Investigator: [name] Site ID # 001	DOCUMENT NUMBER PR# 2022-516 SHEET 24 of 30	REV 1
---	--	--	-------

CLINIMARK Test Plan

Clinical Evaluation of Zynex Monitoring System, Model CM-1600 PR2022-516

- **Adverse Event (AE):** Any untoward medical occurrence, unintended disease or injury, or any untoward clinical signs (including an abnormal laboratory finding) in participants, users, or other persons, whether or not related to the investigational medical device or investigational procedure.
- **Anticipated Serious Adverse Device Effects (ASADE):** ASADE is an effect which, by its nature, incidence, severity, or outcome has been identified in the risk analysis report.
- **Mild:** A mild adverse event is one in which the participant is aware of the event, but it is easily tolerated without intervention.
- **Moderate:** A moderate adverse event is one that causes sufficient discomfort to interfere with usual activities.
- **Serious Adverse Device Effect (SADE):** An adverse device effect results in any of the consequences characteristic of a serious adverse event.
- **Serious Adverse Event (SAE):** A serious adverse event results in death, inpatient hospitalization, severe or permanent disability, a life-threatening illness or injury, fetal distress, fetal death, a congenital abnormality, a birth defect, or requires medical or surgical intervention to prevent permanent impairment to body or structure.
- **Severe:** A severe adverse event results in the inability to perform usual activities.
- **Unanticipated Adverse Device Effect (UADE):** A serious adverse device effect is one which, by its nature, incidence, severity, or outcome has not been identified in the current version of the risk analysis report.

Management of Adverse Event Reporting

Should the participant experience an adverse or non-typical event, the investigational staff will assess the situation and determine appropriate actions. The Medical Director and Principal Investigator will be contacted as appropriate. Adverse Events are reported through standard Clinimark procedures, IRB requirements, and per Zynex SOPs.

Records of adverse events will be recorded in the Case Report Form.

The following information will be obtained:

- Type of effect (ADE, AE, ASADE, SADE, SAE, UADE)
- Date of onset and resolution
- Intensity (mild, moderate, severe)
- Serious (yes/no)
- Relationship to device (unknown, not related, possibly related, probably related, definitely related)
- Anticipated (yes/no)
- Treatment given and / or action taken (procedure stopped, withdrawn from study, no action)

Clinimark [name]	TITLE: Clinical Evaluation of the Zynex Monitoring System, Model CM-1600 ID# PR 2022-516 Principal Investigator: [name] Site ID # 001	DOCUMENT NUMBER PR# 2022-516 SHEET 25 of 30	REV 1
---	--	--	-------

CLINIMARK Test Plan
Clinical Evaluation of Zynex Monitoring System, Model CM-1600
PR2022-516

Reporting of Serious Adverse Events and / or UADE

All SAE's, SADE, ASADE, and UADE will be reported in writing to the Principal Investigator, Medical Director, Sponsor, and IRB as soon as possible and no later than 10 working days after the Investigator first learns of the event.

If the event results in death of a participant, the event shall be reported to the Principal Investigator, Clinimark Medical Director, Sponsor, and IRB within 24 hours of knowledge of the event.

[REDACTED]

Sponsor Records and Reports

Records 21 CFR 812.140 (b) 4,5

The following records shall be consolidated in one location and available for FDA inspection and copying:

- The name and intended use of the device and the objectives of the investigation
- A brief explanation of why the device is not a significant risk device
- The name and address of each Investigator
- The name and address of each IRB that has reviewed the investigation
- A statement of the extent to which the good manufacturing practice regulation in part 820 will be followed in manufacturing the device
- Any other information required by FDA
- Records concerning adverse device effects (whether anticipated or unanticipated) and complaints

Reporting 21 CFR 812.150 (b) 1,2,3,5,6,7,8,9,10:

The Sponsor shall prepare and submit the following complete, accurate, and timely reports:

Unanticipated Adverse Device Effect

The Sponsor shall immediately conduct an evaluation of an unanticipated adverse device effect. The results of such evaluation shall be reported to the FDA, IRB, and participating Investigators as soon as possible and not later than 10 working days after the Investigator first learns of the effect.

Withdrawal of IRB approval

Clinimark [name]	TITLE: Clinical Evaluation of the Zynex Monitoring System, Model CM-1600 ID# PR 2022-516 Principal Investigator: [name] Site ID # 001	DOCUMENT NUMBER PR# 2022-516 SHEET 26 of 30	REV 1
---	--	--	-------

CLINIMARK Test Plan
Clinical Evaluation of Zynex Monitoring System, Model CM-1600
PR2022-516

Withdrawal of IRB approval shall be reported to the FDA, IRB, and the Investigator within 5 working days after receipt of withdrawal of approval by the Sponsor.

Withdrawal of FDA approval

Withdrawal of FDA approval of an investigation shall be reported by the Sponsor to the IRB and the Investigator within 5 working days after receipt of notice of withdrawal of approval.

Progress Reports

The Sponsor shall submit progress reports to the IRB at least yearly.

Recall and device

The Sponsor shall notify the FDA and all reviewing IRBs of any request that an Investigator return, repair, or otherwise dispose of any units of a device. Such notice shall occur within 30 working days after the request is made and shall state why the request was made.

Final Report

The Sponsor shall submit a final report to the IRB with 6 months after termination or completion of the investigation.

Informed consent

The Sponsor shall submit to the FDA a copy of any report by an Investigator under paragraph (a)(5) of this section of use of a device without obtaining informed consent, within 5 working days of receipt of notice of such use.

Significant risk device determinations – (does not apply to NSR studies)

If an IRB determines that a device is a significant risk device, and the Sponsor had proposed that the IRB consider the device not to be a significant risk device, the Sponsor shall submit to FDA a report of the IRB's determination within 5 working days after the Sponsor first learns of the IRB's determination.

Other

A Sponsor shall, upon request by a reviewing IRB or FDA, provide accurate, complete, and current information about any aspect of the investigation.

Investigators Records and Reporting

Records 21 CFR 812.140 (a)(3)(i)

The Investigator maintains records of each participant's case history and exposure to the device and supporting data, including signed and dated consent, health assessment form, and progress notes during the study. Records should show evidence that informed consent was signed and dated prior to the participant engaging in the study.

Reports 21 CFR 812.150 (a) 1,2,5,7

The Investigator shall prepare and submit the following complete, accurate, and timely reports:

Unanticipated adverse device effects

The Investigator shall submit to the Sponsor and to the reviewing IRB a report of any unanticipated adverse device effect occurring during an investigation as soon as possible, but in no event later than 10 working days after the Investigator first learns of the effect.

Withdrawal of IRB approval

Clinimark [name]	TITLE: Clinical Evaluation of the Zynex Monitoring System, Model CM-1600 ID# PR 2022-516 Principal Investigator: [name] Site ID # 001	DOCUMENT NUMBER PR# 2022-516 SHEET 27 of 30	REV 1
---	--	--	-------

CLINIMARK Test Plan
Clinical Evaluation of Zynex Monitoring System, Model CM-1600
PR2022-516

The Investigator shall report to the Sponsor, within 5 working days, a withdrawal of approval by the reviewing IRB of the Investigator's part of an investigation.

Informed consent

If an Investigator uses a device without obtaining informed consent, the Investigator shall report such use to the Sponsor and the reviewing IRB within 5 working days after the use occurs.

Other

The Investigator shall, upon request by a reviewing IRB or FDA, provide accurate, complete, and current information about any aspect of the investigation.

Withdrawal, Early Termination, or Suspension of the Investigation

Participation in the study is voluntary. The participant may choose to withdraw from the study at any point. If a participant officially withdraws from the study, the laboratory staff will document the reason for withdrawal in the case report.

Participation in the study may also be stopped at any time by the Principal Investigator or by the Sub-Investigators or Sponsor for the following reasons:

- The participant's failure to cooperate fully (as determined by the Investigator in his or her sole discretion) with the required conduct of this study
- The participant's development of an illness as determined by the Investigator in his or her sole discretion
- A determination by a Clinimark representative (in his or her sole discretion), for whatever cause, that the study should be discontinued
- A determination by the Sponsor (in his or her sole discretion), for whatever cause, that the study should be discontinued

The collection of data for study participants will cease in the following cases:

- Participant completes all study requirements
- Participant withdraws consent
- Investigator's decision that it is in participant's best interest to be discontinued from the study
- Participant death
- Adverse event other than death requiring withdrawal of the participant from the study
- Determination that the participant was ineligible for the study

No follow-up procedures for withdrawn or discontinued participants are required, unless such is required at the Investigator's discretion.

Consideration for early termination or suspension of the investigation may be related to unanticipated equipment failure or a decision by the Sponsor or the site. Both Zynex and Clinimark reserve the right to discontinue the study at any time for administrative or other reasons. Written notice of study termination will be submitted to the Investigator in advance of such termination. Termination of a specific site may occur because of, but not limited to, inadequate data collection, low participant enrollment, or non-compliance with the protocol or other research requirements.

Early termination results when the study is closed prior to the end of the study. A study suspension is a temporary postponement of the study activities related to enrollment. Both are possible for the study. If the study is terminated or suspended, no additional enrollment will be allowed unless otherwise informed by the Sponsor. The current participants will be followed according to the protocol.

If the study is terminated prematurely or suspended by the Sponsor/Investigator, the Sponsor /Investigator will promptly inform the regulatory authorities (if required) of the termination and the reason(s). IRB/IECs will also be

Clinimark [name]	TITLE: Clinical Evaluation of the Zynex Monitoring System, Model CM- 1600 ID# PR 2022-516 Principal Investigator: [name] Site ID # 001	DOCUMENT NUMBER PR# 2022-516 SHEET 28 of 30	REV 1
---	--	--	-------

CLINIMARK Test Plan
Clinical Evaluation of Zynex Monitoring System, Model CM-1600
PR2022-516

promptly informed and provided with the reason(s) for termination or suspension by the Sponsor/ Investigator. The Investigator will promptly inform the participants and ensure appropriate follow-up for the participant.

If the Investigator (or IRB/IEC) terminates or suspends the investigation, the Investigator will promptly inform the institution (if required) and the IRB/IEC, and will provide a detailed written explanation of the termination or suspension. The Investigator will promptly inform the participants and ensure appropriate therapy and follow-up for the participants. The Sponsor will inform the regulatory authorities (if required).

Withdrawal of IRB approval shall be reported to the Sponsor by the Investigator within 5 working days.

In case of early termination of the study, all study participants should be followed until the resolution of any pending adverse event(s).

[REDACTED]

[REDACTED]

[REDACTED]

Clinimark [name]	TITLE: Clinical Evaluation of the Zynex Monitoring System, Model CM-1600 ID# PR 2022-516 Principal Investigator: [name] Site ID # 001	DOCUMENT NUMBER PR# 2022-516 SHEET 29 of 30	REV 1
---	--	--	-------

CLINIMARK Test Plan
Clinical Evaluation of Zynex Monitoring System, Model CM-1600
PR2022-516

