Attachment A - Protocol Signature Page30

Clinimark [name]
	
TITLE: Clinical Evaluation of the Zynex Monitoring System, Model CM-1600 ID# PR 2022-516 Principal Investigator: [name] Site ID # 001
	
DOCUMENT NUMBER PR# 2022-516 SHEET 5 of 30
	
REV 1

--	--	--	--------------

CLINIMARK Test Plan
Clinical Evaluation of Zynex Monitoring System, Model CM-1600
PR2022-516

Table 1: List of Abbreviations and Definitions of Terms

Abbreviation/Term	Definition
AE	Adverse Event
ANP	Atrial Natriuretic Peptide
BI	Bioelectrical Impedance
BNP	Brain Natriuretic Peptide
BP	Blood Pressure
CM-1600	Zynex Non-invasive Monitoring System CM-1600
CBV	Central Blood Volume
CRF	Case Report Form
CS	Clinically Significant
ECG	Electrocardiogram
cGMP	Cyclic Guanosine Monophosphate
H	Hypotensive Prone
HD	Hemodialysis
HR	Heart Rate
ICW	Intracellular Water Changes
IRB	Institutional Review Board
kg	Kilogram
L	Liter
lb	Pound
LBNP	Lower Body Negative Pressure
mg	Milligram
mL	Milliliter
NCS	Not Clinically Significant
N	Non-hypotensive Prone
NSR	Non-Significant Risk
PO	Pulse Oximetry
PPG	Photoplethysmography
RH	Relative Humidity
SAE	Serious Adverse Event
SR	Significant Risk
TBI	Total Body Impedance
TI	Thoracic Electrical Impedance
ZMS	Zynex Monitoring Solutions

Clinimark [name]	TITLE: Clinical Evaluation of the Zynex Monitoring System, Model CM-1600 ID# PR 2022-516 Principal Investigator: [name] Site ID # 001	DOCUMENT NUMBER PR# 2022-516 SHEET 6 of 30	REV 1
---	--	---	-------

CLINIMARK Test Plan
Clinical Evaluation of Zynex Monitoring System, Model CM-1600
PR2022-516

Summary

Objectives of the Clinical Investigation Plan

The objective of this study is to determine if manual blood loss of up to 500mL of blood and saline re-infusion can be identified using the non-invasive Zynex Monitoring System, Model CM-1600.

[REDACTED]

[REDACTED]

[REDACTED]

[figure not shown]
[figure not shown]
[REDACTED]

[REDACTED]

[REDACTED]

Clinimark [name]	TITLE: Clinical Evaluation of the Zynex Monitoring System, Model CM-1600 ID# PR 2022-516 Principal Investigator: [name] Site ID # 001	DOCUMENT NUMBER PR# 2022-516 SHEET 7 of 30	REV 1
---	--	---	-------

CLINIMARK Test Plan
Clinical Evaluation of Zynex Monitoring System, Model CM-1600
PR2022-516

Protocol Overview

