33. Once data collection on the CM-1600 is stopped, the USB data storage can be removed. USB data storage device is to be labeled in accordance with the assigned participant identification number and the continuity of the acquired data is to be verified and/or backed-up. The CM-1600 device and accessories will be wiped down again with a disinfecting wipe. Electrodes will be disposed.
34. Blood disposal will be carried out at the Investigator site and will follow all applicable rules and regulations, including any site-specific procedures.
35. Clinimark will follow up with the participant in 24-48 hours to screen for any adverse events or complications.

Clinimark [name]	TITLE: Clinical Evaluation of the Zynex Monitoring System, Model CM-1600 ID# PR 2022-516 Principal Investigator: [name] Site ID # 001	DOCUMENT NUMBER PR# 2022-516 SHEET 17 of 30	REV 1
---	--	--	-------

CLINIMARK Test Plan
Clinical Evaluation of Zynex Monitoring System, Model CM-1600
PR2022-516

Statistical Analysis

This is a prospective, single-arm, hypothesis-generating study early in the clinical development of the Zynex CM-1600; hence, no statistical tests are required and no assumptions are made. Any statistical and data analysis will be performed by the Sponsor.

Sample Size Justification

The objective of this study is to determine if manually controlled and quantified blood loss and saline re-infusion can be identified by the non-invasive Zynex CM-1600. No statistical hypotheses have been generated for this study; therefore, the sample size of 20 participants is empirically determined to be sufficient for an early-phase hypothesis-generating study and is based on clinical judgment rather than statistical considerations.

Analysis Populations

This is a hypothesis-generating study of 20 participants; therefore, all data collected will be used and presented in the study summaries.

Statistical Analysis Plan

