- The data for this study will be summarized using descriptive and frequency statistics, depending on the nature of the variable. The distribution of continuous variables will be summarized using number and percentage of non-missing data points, means, standard deviations (sd), medians, minimums, and maximums. Ordinal variables will be summarized using categorical methods if the number of observed responses is small (usually fewer than 4) and with medians, minimums and maximums otherwise. Summary statistics for discrete variables will consist of the numbers and percentages of responses in each category.

Clinimark [name]	TITLE: Clinical Evaluation of the Zynex Monitoring System, Model CM-1600 ID# PR 2022-516 Principal Investigator: [name] Site ID # 001	DOCUMENT NUMBER PR# 2022-516 SHEET 18 of 30	REV 1
---	--	--	-------

CLINIMARK Test Plan

Clinical Evaluation of Zynex Monitoring System, Model CM-1600 PR2022-516

- A descriptive analysis of the change from baseline will be performed to better understand the magnitude of the changes and variability of the measurements for bioelectrical impedance (ohms), heart rate, ECG amplitude, PPG amplitude, skin temperature (°C), to obtain the relative index (RI).
- A correlation analysis will be performed to gain a basic understanding as to how the Zynex CM-1600 measurements relate to the actual volume of blood loss and saline re-infusion. This is a hypothesis-generating study and is not powered to establish a true relationship; therefore, the results of this analysis will not be presented with statistical significance.
- Adverse events and concomitant medications that are reported during the study will be summarized and presented in a tabular format.
- All available data will be presented and summarized based on the number of participants with available data. Missing data will not be imputed, as no statistical inferences will be made based on the results of these analyses.

Investigational Review Board (IRB)/Independent Ethics Committee (IEC)

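### No confidence interval is planned for any estimate: mean changes come with n and SD only, and the correlations with volume with no measure of precision

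*Combined protocol and SAP*

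**What the plan says.** The objective (Objectives of the Clinical Investigation Plan) is to "determine if manual blood loss of up to 500mL of blood and saline re-infusion can be identified" with the CM-1600. The Statistical Analysis section calls the study hypothesis-generating: "hence, no statistical tests are required and no assumptions are made". Under Sample Size Justification, "the sample size of 20 participants is empirically determined to be sufficient for an early-phase hypothesis-generating study", and that number "is based on clinical judgment rather than statistical considerations".

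The Statistical Analysis Plan bullets set out what will be reported:

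- Continuous variables: "number and percentage of non-missing data points, means, standard deviations (sd), medians, minimums, and maximums".
- Change from baseline: "A descriptive analysis of the change from baseline will be performed to better understand the magnitude of the changes and variability of the measurements". It covers impedance, heart rate, ECG amplitude, PPG amplitude and skin temperature, with a view to the Relative Index.
- Correlation of CM-1600 measurements with the actual volumes lost and re-infused: since the study is not powered to establish a relationship, "the results of this analysis will not be presented with statistical significance". The type of coefficient and the unit of analysis are not given.
- Summaries rest on the participants with available data, nothing is imputed, and no inference will be drawn.

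The readable text names no confidence interval or standard error for any estimate.

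**The concern.** The plan treats the small sample as grounds for showing no uncertainty around the correlation. That runs two things together. A significance test needs a hypothesis and, to be useful, adequate power. An interval needs neither: it shows which values the data can and cannot rule out, and it is most informative when the sample is small.

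The study is meant to learn whether blood loss and re-infusion can be picked up by the device, and Protocol Overview describes the result as preliminary data. A coefficient shown alone does not tell the reader whether it reflects a relation worth pursuing or one that 20 people could produce by chance. No lead output is named among the five signals and the Relative Index, so the reader is also not told in advance which coefficient carries the answer.

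**Working it through.** **Inputs.** From the documents: 20 participants, single arm; continuous summaries of n, mean, SD, median, minimum and maximum; no alpha, power, effect size or precision target. Not in the documents, so assumed here: two-sided 95% intervals; one change value per participant; precision expressed in SD units because no SD is given; a range of values for r; and 16 to 20 participants with usable data.

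**The plan's own figure.** The sample size of 20 has no statistical inputs, so there is nothing to reproduce and nothing to call miscalculated.

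**Mean change.** Half-width = t(0.975, n−1) × SD/√n.

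- n = 20: 2.093/4.472 = 0.468, so ±0.47 SD
- n = 18: ±0.50 SD
- n = 16: ±0.53 SD

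Every input to this formula is in the planned output, so a reader can rebuild the interval from the reported mean, SD and n.

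**Correlation, if each participant gives one independent pair.** Fisher z: interval = tanh(atanh(r) ± 1.96/√(n−3)). At n = 20, 1.96/√17 = 0.475. For r = 0.5, atanh(0.5) = 0.549, so the limits are tanh(0.074) = 0.07 and tanh(1.025) = 0.77.

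| Observed r (n = 20) | 95% interval |
|---|---|
| 0 | −0.44 to 0.44 |
| 0.3 | −0.16 to 0.66 |
| 0.5 | 0.07 to 0.77 |
| 0.7 | 0.37 to 0.87 |
| 0.8 | 0.55 to 0.92 |

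At n = 16, r = 0.5 gives 0.01 to 0.80.

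**Does one pair per participant fit the design?** Not clearly.

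- The Method section has data recorded continuously, so a correlation over time within participants is at least as plausible a reading.
- Planned saline is 1 litre for everyone (Procedure, step 25). Between participants, planned saline volume therefore does not vary, and any spread would come from incomplete infusions.
- Planned draw volume is 10% of calculated blood volume with a 500 mL cap (Protocol Overview). The minimum weight of 110 lb is 49.9 kg, which gives 49.9 × 65 × 0.10 = 324 mL for a woman and 49.9 × 75 × 0.10 = 374 mL for a man. The cap is reached at 500/6.5 = 76.9 kg in women and 500/7.5 = 66.7 kg in men, and everyone heavier has the same planned volume.

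If readings over time are used, the Fisher figures above do not apply. Putting the number of pooled readings into that formula would treat repeated readings from one person as independent and give an interval that is falsely narrow.

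**The case against.** The strongest reply is that the plan hides nothing. It says the study is hypothesis-generating and unpowered, has no passing criterion, and will support no inference. It reports n and SD for every continuous variable, and both Analysis Populations and the last Statistical Analysis Plan bullet promise that all data will be presented. This largely stands. It makes the matter a gap in reporting and not a misleading claim. It does not supply a precision measure for the correlations, and absence of power still does not explain why intervals are left out.

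A reader might go further in three ways that the documents do not support.

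- *That mean changes are bare numbers with their chance range concealed.* Mean, SD and n are promised, and they give the interval directly. SD describes spread between people and not the precision of the mean, so printing the interval is still a help.
- *That six outputs by two phases make about a dozen independent chances of a large spurious coefficient.* The plan gives no such count. Planned saline is the same for everyone, and the Relative Index is calculated from the other five signals, so the outputs are not independent.
- *That 0.07 to 0.77 is the chance range of whatever correlation is reported.* It holds only for one independent pair per participant, which is not stated. For the same reason, simply adding a Fisher interval could do harm if readings are pooled.

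Nor do the documents say that a later study will be sized on the SD found here. Limits for the SD, or exact intervals for adverse-event proportions, would be optional extras and are no part of this point.

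**Conclusion.** The point holds as a cheap improvement to reporting. No interval is planned for any estimate. For mean changes this is a convenience lost, since ±0.47 SD at 20 participants can be rebuilt from planned output, given one change per participant and an approximately normal mean. For the correlations it is a real gap, because no measure of precision is planned and neither the coefficient nor the unit of analysis is stated.

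Under one independent pair per participant, an r of up to about 0.44 in size would be compatible with no relation. If readings over time are used, the precision cannot be worked out from r and n at all, which makes it more important that the sponsor plan the interval. The decision to show no p-values is sound and should stay.

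**What to change.** Leave the clause that withholds significance in place and add after it:

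> Each change from baseline and each correlation is reported with a two-sided 95% confidence interval, labelled descriptive. Correlations use the participant as the unit: a repeated-measures correlation, mixed model or participant-level bootstrap where readings over time are used, and Fisher z only where each participant contributes one pair. The Relative Index is the lead output, the five input signals are supportive, and every correlation computed is shown.

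The same bullet should name the coefficient used. Sample Size Justification may add that 20 participants give a mean change to ±0.47 SD. It should not state an interval for a correlation, because that depends on a unit of analysis not yet fixed.

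The change needs SAP wording and a little more analysis work, with no new data and no change to what participants undergo. The downside is that the intervals will be wide and the results will look less favourable.
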